9.3 Steps to ensure security of data to maintain confidentiality

PROTOCOL TITLE: Treating cognitive impairments in cancer patients via systematic light exposure

Biological samples will be de-identified with personal participant information before lab staff begin processing. Each participant will be assigned a unique ID# for the study. Lab staff will only have access to the ID# and date/time of collection of samples.

Confidentiality of each participant's medical, neuropsychological test data, questionnaire and interview data will be protected with utmost care. All paper-and-pencil research data will be identified by ID# only and stored in locked filing cabinets. Physical consent forms and tracking data (e.g., contact information) will be stored separately in locked filing cabinets. To ensure confidentiality, a "cross-over" file matching ID# with participant identifying information (name, address and phone number) will be maintained and stored separately from the data with password protection. Only study personnel will have access to the cross-over file.

Data from RedCap will be accessible to research study team members using password protection and will only be identified by participant ID#.

The use of email will be in accordance with Northwestern policy (i.e. secure email, obtaining consent from subject to send email, etc.).

Electronic research and tracking data will be stored on a secured Northwestern University network drive. All study personnel will undertake required CITI, HIPAA and Data Safety and Monitoring courses through Northwestern. The PI and research assistant will be responsible for secured receipt and transmission of all aforementioned data and only study personnel will have access to it. Upon completion of the study, the data files will be fully anonymized and the links between patients to the codes will be deleted.

9.4 Procedures for quality control of collected data

The PI will collect data from the first participant to ensure the procedures are clean. The research assistant will then be rigorously trained by the PI to undertake all assessments and will observe the research assistant administer assessments until he/she is fully trained.

After the completion of each interview, the research assistant will be required to carefully check all recorded answers, correct any possible errors and conduct re-questioning if necessary. The research assistant will sign his/her name on the front page of each questionnaire in order to be accountable for the quality of the data collection. The PI will check the scoring of the first 3 neuropsychological assessments and will randomly check 5 more during the course of the study.

Study scripts and questionnaires have been designed for ease of administration and to minimize confusion and data entry errors.

The PI and research assistant will meet at least once a week to discuss study procedures and any issues.

Results from RedCap are immediately captured by their software thus minimizing data entry errors.

10.0 Provisions to Monitor the Data to Ensure the Safety of Subjects

The proposed study does not involve more than minimal risk to subjects.

10.1 Monitoring the progress of trials and the safety of participants.

PROTOCOL TITLE: Treating cognitive impairments in cancer patients via systematic light exposure

The proposed research is a low-risk behavioral trial. Study staff will be available to participants who have any difficulty with their equipment or any unexpected reaction during the intervention period. If a participant experiences minor side effects (e.g., sleep disturbance, headache, eye strain or 'stinging' sensation in the eyes, nausea, and hyperactivity), study staff will work with the participant to ensure they are using the Litebook correctly and for no longer than the prescribed length of time. If the side-effects do not abate within three days, the participant will be discontinued from the intervention. If a participant experiences a more serious side effect (e.g., mania), then the participant will be discontinued from the study immediately and referred to their physician for follow-up. Study staff will be required to report all serious adverse events to Northwestern University's IRB according to policies and procedures outlined by that body. Study staff are also responsible to report all adverse events to the study PI as well. As per Northwestern's IRB policies, the study PI is required to notify the IRB promptly of any unanticipated problems involving unanticipated adverse events and risks to subjects or others that occur. The study staff PIs will monitor the progress of the trial and safety of participants on an ongoing basis. The procedures of this study will ensure discussion and reporting of all possible outcomes including adverse events. If the adverse event is due to the intervention and is unexpected, the PI will draft a safety report and send a copy to the Northwestern IRB. The IRB committee will serve as an objective review mechanism. This policy/procedure means that any potential conflict of interest inherent in the PI being the sole reviewer of unanticipated is avoided. We will use screening procedures used in our prior studies with HSCT survivors to assess depression/suicidality. If risk of suicidality or severe depression is revealed, our staff psychologist will contact the participants the same day, take emergency steps and make referrals as needed.

11.0 Withdrawal of Subjects

11.1 Anticipated circumstances under which subjects will be withdrawn

If there is any significant worsening of a subject's medical or psychiatric condition that is likely due to participation in the study, then the subject will be withdrawn immediately.

Subjects will be allowed to withdraw from the research at any time. They will also be allowed to skip any questions or questionnaires.

11.2 Procedures for orderly termination

Procedures related to handling unexpected adverse events (Section 9.1.2) will be followed.

11.3 Procedures that will be followed when subjects withdraw from research

If a participant has already begun participation in the study, but then refuses to complete one aspect of data collection (e.g., blood collection), that person will be permitted to continue in the study to completion at the discretion of the PI.

12.0 Risks to Subjects

12.1 Risks related to subjects' participation in research

The proposed project is a low-risk primarily behavioral study. There always exists the potential for loss of private information; however, all possible precautions will be set in place in order to prevent loss of confidentiality. There is also a chance that they will experience potential side effects of light therapy, e.g., sleep disturbance, headache, eyestrain, nausea, and hyperactivity, though this is rare. They will be informed that such side effects are usually minimal (i.e., not clinically significant) if the light is positioned correctly and resolve quickly. During the course of the protocol, if side effects persist, we will withdraw them from the study. There is also a chance participants will feel some distress or discomfort as a result of answering some questions asked during the study or completing the neuropsychological assessment. Past research has shown that such distress is usually minimal and transient. There are minimal risks associated with blood draws, including pain, bruising, swelling, dizziness, or infection. Some people feel dizzy or may faint during or after a blood draw.

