6.0 Study Endpoints

6.1 The primary endpoints in the proposed study are: 1) the level of cognitive functioning (as measured by the neuropsychological tests and self-reported cognitive functioning using the PAOFLI)

Secondary endpoints are: 1) Circadian activity rhythms using an actigraph (a small device similar in size to a watch that measures sleep and wake activity); 2) The Pittsburgh Sleep Quality Index; 3) the FACIT Fatigue Scale; 4) Quality of Life measured by the SF-36 scale; 5) a Credibility/Expectancy Questionnaire; 6) levels of Inflammatory Immune Markers; 7) the amount of time that the light boxes are used; 8) treatment satisfaction using the FACIT-TS-G scale; 9) depressed mood as measured by the CES-D; and 10) neurobehavioral functioning as measured by the Frontal Systems Behavior Scale.

6.2 With regard to safety endpoints, there are no known risks associated with the use of the light boxes in the treatment of cognitive impairments. However, we will monitor those who decide to cease treatment because they find the treatment approach unacceptable along with their concerns regarding treatment.

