Time 4 (8 weeks after the intervention) – The study team will send the actigraph and sleep logs to participants again 7 weeks after the intervention. During the eighth week after the intervention, the participant will be asked to wear the actigraph again for 7 days and complete sleep logs. Then the participant will be asked to come in to Northwestern Medicine again to complete the same procedures as at Time 2, except their blood will not be drawn at this appointment.

Note that the neuropsychological testing portion of each assessment will be audio recorded with the permission of the participant to optimize scoring accuracy by the study team. Participants can still participate in the study even if they choose not to be recorded.

Data about subjects will be collected from medical charts, interview questions, questionnaires that the participants will be administered in-person and via online portal (RedCap), output from the equipment (i.e., actigraph data), and blood samples. All questionnaire data collected through RedCap will be coded to each subject's unique study ID. RedCap will not collect any identifiable information and will not log the participants' IP addresses. Neuropsychological testing will be audio-recorded when permission is given by the participant, and those audio files will also be coded to each subject's unique study ID.

Subjects who wish to receive feedback about their neuropsychological test scores may receive a debriefing from the PI at the end of their participation upon request.

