7.2.1 Procedures performed to lessen the probability or magnitude of risks

Please see the Data Safety and Monitoring Plan in Section 10.0 for procedures taken to lessen the probability or magnitude of risks.

7.2.2 Source records used to collect data about subjects.

PROTOCOL TITLE: Treating cognitive impairments in cancer patients via systematic light exposure

Data about subjects will be collected from medical charts, interview questions, questionnaires, blood samples, and output from the equipment (i.e., actigraph data and integrated meter data from the light boxes). Questionnaires will be administered in person and via an online portal (RedCap).

Participants who self-refer will be provided a release of information to access their medical chart from other institutions.

All data collected through RedCap will be coded to each subject's unique study ID. Any identifiable information will be coded in RedCap as an "identifier." This allows the study team to export ONLY deidentified data, whilst preserving the ability to run the study effectively (i.e., being able to access participant contact information and recording study-related communications). Redcap will not log the participants' IP addresses. Surveys, scripts and data collection forms are attached.

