- 5) **Cognitive Screening (Screening):** Participants will be asked whether they have concerns about their cognition by asking a question derived from the two cognitive questions on the

PROTOCOL TITLE: Treating cognitive impairments in cancer patients via systematic light exposure

European Organization for Research and Treatment of Cancer Quality of Life Questionnaire (EORTC QLQ C-30).

- 6) **Neuropsychologically-assessed Cognitive Functioning (Times 1, 3, and 4):** Standardized neuropsychological tests will be used to evaluate multiple cognitive domains. They include all of the tests recommended by the International Cognition and Cancer Taskforce in their Lancet article⁶ chosen due to their frequent use in CRCI assessment and appropriateness for repeat assessments over time: a) Premorbid Intellectual Function will be assessed using the Wechsler Test of Adult Reading and the Vocabulary subtest of the Wechsler Adult Intelligence Scale - 4th Ed. (WAIS-IV) at Baseline only; b) Psychomotor vigilance will be assessed with the Psychomotor Vigilance Task; c) Attention will be assessed with the Digit Span subtest of the WAIS-IV;⁹⁹ d) Visual motor performance will be assessed with the Grooved Pegboard Test and Block Design subtest of the WAIS-IV; e) Visuospatial ability will be assessed with the Rey Complex Figure Test. f) Sustained attention and vigilance will be assessed with the Conners Continuous Performance Test 3rd Edition will be used to assess sustained attention and vigilance; g) Information processing will be assessed with Trail-Making Test A.¹⁰⁰ h) Processing speed will be measured with the Coding subtest of the WAIS-IV; i) Verbal fluency will be assessed with the Verbal Fluency subtest of the Delis-Kaplan Executive Function System (D-KEFS). j) Verbal learning and Memory will be assessed with the Hopkins Verbal Learning Test - Revised.¹⁰² k) Visual learning and memory will be assessed with the Brief Visuospatial Memory Test – Revised. l) Executive Function will be assessed with Trail-Making Test B¹⁰⁰ and the Paced Auditory Serial Addition Task¹⁰³ and the Stroop Color and Word Test.

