9.0 Data and Specimen Management

9.1 Data analysis plan

Descriptive statistics will be calculated for the entire group and separately for each treatment group. T-tests and Fisher's exact tests will be used to assess group differences at baseline for possible confounders (i.e., demographic variables, and clinical characteristics *including time since transplant*). Variables showing differences between the two groups will be used as covariates in subsequent analyses. Since there is no known seasonality effect on cognitive functioning, seasonality will not be controlled in these analyses.

Aim 1: Assess the feasibility and acceptability of BWL as an intervention for CRCI in HSCT survivors. Feasibility: We will adhere to currently accepted practice for feasibility studies¹¹⁰ by measuring the number of eligible patients, willingness of participants to be randomized, follow-up rates, the number who cease the intervention and their specific concerns about the intervention. We will monitor adherence by examining integrated meter data (i.e., time and duration of light box use). We expect high adherence, but if there is variation in duration, we will use duration as a predictor of the outcomes. Participants will be asked to log light box use (beginning and ending time) and reasons for not using it if that occurs. There is no gold standard for what constitutes a “feasible” study and relevant CRCI intervention feasibility studies have not been home-based.^{18, 111} Nevertheless, in an inpatient cognitive rehabilitation study of HSCT patients, 78% completed baseline, intervention, and time 2 assessments.¹⁸ A light exposure feasibility study for seasonal affective disorder deemed a 68% completion rate as acceptable,¹¹² and this is the criteria we will use in this study. In [name]'s pilot study, breast cancer

PROTOCOL TITLE: Treating cognitive impairments in cancer patients via systematic light exposure

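### Section 12.1 withdraws participants with persistent minor side effects from the study, while Section 10.1 stops only the light; 12.1 should follow 10.1, with assessments continuing

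*Combined protocol and SAP*

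**What the plan says.** Section 12.1 names sleep disturbance, headache, eyestrain, nausea and hyperactivity as possible effects of the light, calls them rare, and then states: "During the course of the protocol, if side effects persist, we will withdraw them from the study".

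Section 10.1 gives nearly the same list, labels the effects minor, and has staff first check that the device is being used correctly. It then says: "If the side-effects do not abate within three days, the participant will be discontinued from the intervention". The next rule covers a different class of event: "If a participant experiences a more serious side effect (e.g., mania), then the participant will be discontinued from the study immediately".

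Section 7.2.1 says which section governs risk procedures: "Please see the Data Safety and Monitoring Plan in Section 10.0 for procedures taken to lessen the probability or magnitude of risks".

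Three other parts of the plan depend on which rule is applied:

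- **Feasibility (Section 9.1, Aim 1).** The list of measures includes "follow-up rates, the number who cease the intervention and their specific concerns about the intervention", so staying in follow-up and staying on the light are counted separately.
- **Primary endpoint (Section 6.1).** It combines neuropsychological tests with "self-reported cognitive functioning using the PAOFLI".
- **Schedule (Sections 7.1.1 and 7.3).** The test battery is listed as "Neuropsychologically-assessed Cognitive Functioning (Times 1, 3, and 4". Self-reported cognition is also collected at Time 2. The last assessment is "Time 4 (8 weeks after the intervention".

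**The concern.** Staff dealing with a headache that does not settle have two instructions, and these lead to different data. Under 10.1 the participant has ceased the intervention and nothing more. Under 12.1 the same participant also leaves follow-up, by rule and not by choice, and the two Aim 1 counts are merged for that case.

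The loss also reaches the primary endpoint. There is no neuropsychological test between baseline and the fourth treatment week, so withdrawal during treatment leaves only the baseline score. The reason for the loss is related to treatment and could differ between arms, since the bright device emits about 1000 lux and the dim one under 50 (Section 7.1.1). Section 9.1 relies on a likelihood-based mixed model to avoid a completers-only analysis. That model uses every observed score, but it corrects for the loss only if observed data explain it.

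**Working it through.** The plan gives no figure for this point, so there is none to reproduce. The check compares the rules and then sizes the consequences.

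**1. The rules side by side**

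| Section | Event | Disposition |
|---|---|---|
| 10.1 | Minor effects still present after three days | Off the intervention |
| 10.1 | More serious effect, such as mania | Off the study |
| 11.1 | Marked medical or psychiatric deterioration attributed to the study | Off the study |
| 11.3 | Refusal of one part of data collection | May stay, at the PI's discretion |
| 12.1 | Persistent side effects, nearly the same list as the first row | Off the study |

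The first and last rows describe the same event and give different dispositions. Sections 11.1 and 11.3 cover other events and do not settle the difference. Because 10.1 uses two different dispositions and 7.2.1 refers readers to Section 10.0, 12.1 is the outlier.

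**2. Cognitive scores available (Section 7.3)**

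| Case | Neuropsychological tests | Self-report |
|---|---|---|
| Withdrawn under 12.1 before Time 2 | Time 1 only | Time 1 only |
| Withdrawn under 12.1 between Times 2 and 3 | Time 1 only | Times 1 and 2 |
| Light stopped under 10.1, assessments continue | Times 1, 3 and 4 | Times 1 to 4 |

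**3. Follow-up rate.** With 80 participants, each one lost lowers the rate by 1/80 = 1.25 percentage points, provided that the person would otherwise have attended.

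**4. Efficacy, as an illustration only.** The plan gives no withdrawal rate. Assumptions: 40 per arm; 0 to 2 lost per arm; and a shortfall g of 0 to 0.33 SD in those lost, compared with similar participants who stay in the same arm. The upper value is the pilot difference in ten patients (Section 2.2). With w the share of an arm lost, B bright and D dim:

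bias = wB × gB − wD × gD

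| Lost, bright | Lost, dim | g (SD) | Bias (SD) |
|---|---|---|---|
| 2 | 0 | 0.33 | 2/40 × 0.33 = +0.0165 |
| 2 | 0 | 0.165 | 2/40 × 0.165 = +0.008 |
| 2 | 1 | 0.33 | 0.0165 − 0.00825 = +0.008 |
| 2 | 2 | 0.33 | 0 |
| 0 | 2 | 0.33 | −0.0165 |

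If the loss depends only on the baseline score, which the model sees, the bias is essentially zero. For scale, take the plan's autocorrelation of 0.60 as the correlation between baseline and Time 3, with unit SD. The baseline-adjusted standard error is then sqrt((2/40) × (1 − 0.36)) = sqrt(0.032) = 0.179 SD. The largest bias is 0.0165/0.179, about 9% of one standard error.

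**5. Timing of Time 4.** One baseline week, four treatment weeks and eight further weeks make 13. This matches the lower end of the 13 to 15 weeks in Section 5.1, which vary only with return of equipment.

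**The case against.** The strongest case on the other side is that the plan already does most of what is asked. Section 7.1.1 sets assessments for participants in both arms and makes no exception for those who stop the light. Section 9.1 counts follow-up apart from cessation and would use duration of light use as a predictor, so partial users are expected in the analysis. Section 12.1 is a risk summary without a time limit or procedure, and readers are sent elsewhere for procedures. This largely stands. A reader might infer that the plan has no intention of following those who stop; the documents do not support that. The explicit statement on continued assessment is a clarification. What remains is that 12.1 says the opposite and nothing corrects it.

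The sentence in 12.1 could also describe a later step: the light is stopped first, and the participant is withdrawn if the effects continue even then. That is possible but not the natural reading. Section 12.1 mentions no earlier step, and 10.1 has no later one.

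A reader might infer that Time 4 is undefined for early stoppers. Read alone, its definition is ambiguous, but Section 5.1 points to the planned calendar.

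A reader might also infer that the 68% completion criterion is at risk. Section 9.1 does not define completion. If completing the intervention is part of it, someone who stops the light is a non-completer under either section. If only assessments count, 25 of 80 could be lost before the rate falls below the mark (55/80 = 68.75%; 54/80 = 67.5%).

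Finally, the sentence in 12.1 is itself a participant protection, so changing it is a decision for the investigator and the IRB. That stands.

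**Conclusion.** The conflict is real and worth removing, but its effect is small. Sections 10.1 and 12.1 treat the same event differently, and following 12.1 would discard Time 3 and Time 4 primary-endpoint data for a treatment-related reason. The cost to follow-up is at most 1.25 percentage points per affected participant, and only for those who would have attended; anyone may leave under Section 11.1.

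A reader might infer a material bias in the comparison of bright and dim light. The documents do not support that. Section 12.1 calls side effects rare, and Section 7.1.1 reports no adverse events in an earlier study with the same devices. The illustrated bias of at most 0.017 SD has either sign, and it rests on an assumed number of losses and a shortfall borrowed from a ten-patient breast cancer pilot. The expected bias is negligible. The case for the change rests on one consistent instruction, separate feasibility counts and retained scores.

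**What to change.** Reword Section 12.1 so that persistent minor side effects lead to stopping the light treatment as described in Section 10.1. State in 10.1 and 12.1 that, with the participant's agreement, the remaining scheduled assessments continue on the originally planned calendar and are analysed in the randomised arm. Leave the three-day rule, the rule for serious effects, Section 11.1 and the right to withdraw unchanged.

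The cost for each participant who stops early is:

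- the remaining questionnaires, including Time 2 if it is still ahead
- two visits (Times 3 and 4)
- two seven-day actigraphy periods with sleep logs
- the Time 3 blood draw
- payments at $60 per completed assessment (Section 19.1): 2 × $60 = $120 if two of the remaining assessments are paid, or 3 × $60 = $180 if all three are. Section 19.1 lists Times 1, 2 and 3, so how it applies to Time 4 has to be assumed.

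The change also needs a protocol amendment, because it alters a withdrawal sentence. If the consent form repeats that sentence, it needs revision too; the consent pages were not available to check.
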